3.7. Outcome Measurements & Timeline

Participant-Reported Overall Health: measured using the EuroQol visual analogue scale (EQ-VAS).⁵⁹ The EQ-VAS records the respondent’s overall current health on a vertical scale between 0 and 100, where the end points are labelled “the best health you can imagine” (i.e., a score of 100) and “the worst health you

can imagine" (i.e., a score of 0). The EQ-VAS will be filled out each day while on the intervention (21 days total).

Health Status: Measured by combining one level from each of the five dimensions of the EuroQol 5-dimension 5-level (EQ-5D-5L) questionnaire⁵⁹ (mobility, self-care, usual activities, pain/discomfort, and anxiety/depression) to form a unique health state. Each dimension is divided into five levels of perceived problems: 1 – no problem, 2 – slight problems, 3 – moderate problems, 4 – severe problems, and 5 – unable to perform/extreme problems. The EQ-5D-5L questionnaire will be filled in at baseline (i.e., before starting the intervention) and weeks 1, 2, 3, 4, 8, and 12.

Symptom Severity & Duration: Measured using an internally-developed questionnaire specific for the most common COVID-19 symptoms, which include: fever, cough, shortness of breath, fatigue, headache, myalgia/arthralgia (body aches), nausea, vomiting, diarrhea, chills, altered taste, altered smell, and nasal congestion.^{11,60} Each symptom will be rated based on severity with a 4 point scale (0-3): 0-none, 1-slight, 2-moderate, and 3-severe. Participants will fill in this questionnaire each day while receiving treatment (i.e., for 21 days).

The questionnaire is largely based on recommendations from the US Food and Drug Administration (FDA) guidance document for investigators conducting community clinical trials for COVID-19 prevention or treatment.⁶¹ The symptoms were selected based on the most commonly reported COVID-19 symptoms in both the hospital and community setting.^{11,60} Some of the same symptoms are also included in the questionnaire being used in a study of vitamin C and zinc (COVIDAtz) at the Cleveland clinic, potentially allowing for comparison of results.²⁹

Incidence of delayed return to usual health: Measured through follow-up calls with participants after the treatment period has ended. Participants will be contacted at weeks 4, 8, and 12 to assess this. The incidence of delayed return to usual health will be defined as the presence of any symptoms related to COVID-19 at the time of these calls as reported by the participant. Those experiencing prolonged COVID-19 symptoms lasting 4-12 weeks will be classified as experiencing "ongoing symptomatic COVID-19," while those still afflicted at 12 weeks will be classified as having "post-COVID-19-syndrome."⁶²

Hospitalization: the rate and type of hospitalization, as well as the length of stay, will be collected from participant medical records where possible and will otherwise be self-reported. Information will be collected throughout the 12-week study period.

All-Cause Mortality: date of death will be collected through medical records and obituary searches when medical records are not available. Information will be collected throughout the 12-week study period.

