3.1. Study Design

This study is a double-blind, placebo-controlled, phase III randomized controlled trial powered to detect meaningful differences in the overall health and symptom severity of people with COVID-19 between the treatment and control arms. Eligible participants will be randomly assigned, using a web randomization system, in a ratio of 1:1 to one of the following groups: (1) nutrient therapy with vitamin D, vitamin C, vitamin K2, and zinc or (2) placebo. Total trial duration will be 12 weeks. Nutrients or placebo will be given for a period of 21 days following enrolment and randomization. The length of the intervention period (21 days) encompasses the most common period within which recovery occurs. The median duration of time to symptom resolution is 4-8 days from testing and yet a substantial number of people (26-47%) do not return to their usual state of health within 14-21 days.³³ Available guideline recommendations support a prolonged follow up period in order to assess patients experiencing ongoing symptomatic COVID-19 (signs and symptoms for 4-12 weeks) and those with post-COVID-19 syndrome (signs and symptoms >12 weeks).³⁴

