3.7.2. Measurement of Fever

Temperatures will be taken by the participant using a digital oral thermometer provided by the research staff. Participants will be instructed to wait 30 minutes after consumption of any fluids before taking their temperature. Consumption of fluids, especially cold,⁶³ can alter oral temperature readings by clinically meaningful amounts for up to 30 minutes,^{63,64} which, if unaddressed, may lead to measurement errors.

Table 1: Schedule of Events

	Time of Assessment										
	Screening (pre-enrolment)	Baseline (Prior to intervention)	Days 1-6	Day 7	Days 8-13	Day 14	Days 15-20	Day 21	Week 4	Week 8	Week 12
Eligibility	✓										
Informed Consent	✓										
Randomization		✓									
Medical History & Current Medications		✓									
Demographics		✓									
Study Intervention			✓	✓	✓	✓	✓	✓			
EQ-VAS			✓	✓	✓	✓	✓	✓			
Symptom Questionnaire			✓	✓	✓	✓	✓	✓			
EQ-5D-5L		✓		✓		✓		✓	✓	✓	✓
Phone Call Follow-Up • Concomitant Medications • Adverse Events • Hospitalizations • Delayed return to usual health				✓		✓		✓	✓	✓	✓

EQ-VAS: EuroQol Visual Assessment Scale; EQ-5D-5L: EuroQol 5-Dimension 5-Level. EQ-VAS and symptom questionnaires must be filled in on the appropriate days. A 3-day window will be allowed for EQ-5D-5L completion and phone call follow-up for the first 4 weeks. The window will increase to 5 days for weeks 8 and 12. Compliance to the intervention will be participant-reported and take place on day 21 or week 4.

Table 2: Outcome Assessment Methods

Objective	Assessment Method
Participant-reported health	EQ-VAS
Health Status	EQ-5D-5L
Symptom severity & duration of COVID-19 symptoms	Internally developed questionnaire
Incidence of delayed return to usual health	Call with participants
Incidence of Hospitalizations, including ER, acute care, and ICU admissions.	Data will be gathered through medical records and through calls with the participant
Length of Stay	
Incidence of Mortality	Data will be gathered through medical records or through obituary searches if medical records are not available

4. Study Conduct

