6.2.1.3. Incidence of Delayed Return to Usual Health

The incidence of participants experiencing ongoing symptomatic COVID-19 and post-COVID-19 syndrome will be compared between both arms.

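### Symptoms present on the day of the week 4, 8 and 12 calls cannot show that symptoms lasted, yet they are used to assign the class of symptoms lasting 4 to 12 weeks

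*Combined protocol and SAP*

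**What the plan says.** Section 3.7 (Outcome Measurements & Timeline) sets the schedule: "Participants will be contacted at weeks 4, 8, and 12 to assess this". The case definition is "presence of any symptoms related to COVID-19 at the time of these calls as reported by the participant".

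Two classes follow. The first is worded as a duration: "Those experiencing prolonged COVID-19 symptoms lasting 4-12 weeks will be classified as experiencing" ongoing symptomatic COVID-19. The second is worded as a status: "those still afflicted at 12 weeks will be classified as having" post-COVID-19 syndrome. Section 3.1, citing guideline recommendations, words both as durations: "ongoing symptomatic COVID-19 (signs and symptoms for 4-12 weeks) and those with post-COVID-19 syndrome (signs and symptoms >12 weeks").

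The only repeated symptom record is the daily questionnaire, and it ends with treatment: "Participants will fill in this questionnaire each day while receiving treatment (i.e., for 21 days"). Table 2 lists one method for this outcome: "Incidence of delayed return to usual health Call with participants".

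For the analysis, section 6.2.1.3 says: "The incidence of participants experiencing ongoing symptomatic COVID-19 and post-COVID-19 syndrome will be compared between both arms". Section 6.2.2 names the chi-square or Fisher's exact test. No section gives a look-back question, a start or stop date for symptoms after day 21, a rule for combining the three calls, or a rule for intermittent symptoms.

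**The concern.** The measurement and the class do not match. A call-day answer is a point observation, whereas the ongoing class is a statement about an interval. The plan recognises relapse in the 21-day outcome, where section 6.2.1.2 counts symptoms as resolved only if they do not return. It has no counterpart for the long-term outcome.

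Two errors are possible:

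- A participant whose symptoms come and go may be well on the call day and be missed.
- A participant with symptoms on one call day may be labelled as having had them for weeks.

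At stake is the interpretation of one listed secondary objective, which section 3.1 also uses to justify the prolonged follow-up. The history between calls, if not asked for at the time, cannot be reliably recovered at analysis.

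**Working it through.** **Step 1: is there another source of post-day-21 symptom data?**

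- Symptom questionnaire: ends at day 21 (section 3.7, Table 1).
- EQ-5D-5L at weeks 4, 8 and 12: covers mobility, self-care, usual activities, pain/discomfort and anxiety/depression. It has no COVID-19 symptom list.
- Adverse events: non-serious COVID-19 symptoms such as cough and fatigue are not recorded (section 7.2.1). Gastrointestinal events are recorded, but collection stops one week after the intervention apart from expedited events (section 7.2).

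These are partial sources. None can supply the duration needed for the class.

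**Step 2: what the call can show for each class.**

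- Ongoing class: a positive call shows presence on that day, not persistence, so over-classification is possible. A negative call does not show absence between calls, so under-classification is possible. The net direction cannot be derived from the documents.
- Post-COVID-19 class: this is a status at week 12, decided by one call. The error from intermittent symptoms runs one way: cases who are well that day are missed.

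**Step 3: chance of missing an intermittent case.** The plan gives no figure for this outcome to reproduce, so what follows is illustration. Let q be the fraction of days on which an intermittent case has symptoms, with calls independent. Then P(missed at one call) = 1 − q and P(missed at all three) = (1 − q)³.

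| q | missed at one call | missed at all three |
|---|---|---|
| 0.5 | 50% | 12.5% |
| 0.8 | 20% | 0.8% |

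**Step 4: effect on power.** Let r be the share of true cases that are intermittent.

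- Sensitivity of one call: 1 − r(1 − q).
- Sensitivity if any of three calls counts: 1 − r(1 − q)³.
- Power = Φ[(d − 1.96·SE₀)/SE₁], where d is the difference in observed rates, SE₀ = √(2p̄(1 − p̄)/n) and SE₁ = √([p₀(1 − p₀) + p₁(1 − p₁)]/n).
- n = 88 per arm is taken from section 5, where it was set for the primary outcome. Two-sided 0.05 is assumed, as the plan does not state sidedness. The true rates (30% versus 12%), r and q are assumptions.

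Full detection: d = 0.18, p̄ = 0.21, SE₀ = 0.0614, SE₁ = 0.0599. Power = Φ(0.996) = 84%.

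r = 0.5, q = 0.5, one call: sensitivity 0.75, observed 22.5% versus 9.0%, d = 0.135, SE₀ = 0.0549, SE₁ = 0.0540. Power = Φ(0.507) = 69%.

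| r | q | rule | sensitivity | observed rates | power |
|---|---|---|---|---|---|
| 0.5 | 0.5 | one call | 0.75 | 22.5% vs 9.0% | 69% |
| 0.5 | 0.8 | one call | 0.90 | 27.0% vs 10.8% | 79% |
| 0.5 | 0.5 | any of three | 0.94 | 28.1% vs 11.3% | 81% |
| 0.5 | 0.8 | any of three | 0.996 | 29.9% vs 12.0% | 84% |
| 1.0 | 0.5 | one call | 0.50 | 15.0% vs 6.0% | about 50% |
| 1.0 | 0.8 | one call | 0.80 | 24.0% vs 9.6% | 73% |

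The one-call rows apply to post-COVID-19 syndrome. The any-of-three rows apply to delayed return as a whole, and only if one positive call suffices, which the plan does not state. The ratio of observed rates stays at 2.5 throughout; it is the absolute difference and the power that shrink.

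The result is sensitive to the assumed rates. With 30% versus 15%, full-detection power is 67%. It becomes 51% on one call at r = 0.5 and q = 0.5, and ranges from 63% down to 31% as r and q each run over 0.25 to 0.75.

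**Step 5: would a wider recall window solve it?** A question on any symptom in the last 7 days would find more intermittent cases but also unrelated symptoms. With full sensitivity and an assumed false-positive rate of 10%, observed rates become 0.30 + 0.70 × 0.10 = 37.0% and 0.12 + 0.88 × 0.10 = 20.8%, and power is 66%. Replacing the definition could therefore cost as much as it gains.

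**The case against.** Several points stand against a stronger reading.

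- A reader might infer that anyone well at a call is counted as recovered. The plan has no such category. A participant well at one call escapes delayed return altogether only if also negative at the other two, should any positive call count. A participant well at week 12 but positive earlier could still fall in the ongoing class.
- A reader might infer that both classes are understated. That is not established. The inability to show duration also permits over-classification of the ongoing class. Understatement from this source is clear only at week 12.
- A reader might infer that both classes are defined as durations. Section 3.7 words post-COVID-19 syndrome as a status at 12 weeks, which a week 12 call does measure. Only section 3.1 words it as a duration.
- A reader might infer a large power loss. The largest losses at 30% versus 12% require every case to be intermittent, and the documents supply neither the relapsing share nor the week 12 rates.

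It can also be said that a participant with on-and-off symptoms may answer yes when well that day, and that the case report forms or Procedures Manual may contain a fuller question. Both are possible, but the written definition does not require it. The outcome is one of seven secondary objectives and carries no power claim.

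These points limit the direction and size of the concern. They do not remove the mismatch between a call-day measurement and a duration class.

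**Conclusion.** The point holds in limited form. The stated measurement cannot support the class of symptoms lasting 4 to 12 weeks, and no other scheduled record fills the gap. For that class the net bias is of unknown direction. For post-COVID-19 syndrome, intermittent cases who are well on the call day are missed; both arms' rates fall and some power is lost. The illustrative loss is about 5 to 15 percentage points (84% to 79% or 69%), resting on assumed rates of 30% versus 12%, half of cases relapsing, and symptoms on 50% to 80% of days. Because the trial is blinded, the misclassification should be mainly non-differential. The primary EQ-VAS result is not affected. This is a cheap improvement to a secondary outcome.

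**What to change.** In section 3.7:

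1. Keep call-day presence as the recorded definition.
2. At the existing week 4, 8 and 12 calls, add: have COVID-related symptoms been present, continuously or on and off, since the last call, and on what date were they last present?
3. Use that answer to assign the class of symptoms lasting 4 to 12 weeks.
4. State how the three calls combine, and that a participant still affected at week 12 is counted in the post-COVID-19 class, so that the two classes do not overlap.

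In section 6.2.1.3, add a last-7-days version of week 12 status as a sensitivity analysis only. It can be derived from the date last present.

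The cost is one short two-part question on calls already scheduled, with changes to protocol and case report form wording. There is no new visit or instrument. The downside is recall error, over about four weeks at the week 8 and 12 calls, and some capture of unrelated symptoms. Keeping call-day presence as the recorded definition limits both.

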3.7.1. Phone Calls

Follow-up calls will take place during weeks 1, 2, 3, 4, 8, and 12 to assess for outcomes, compliance, and as a general check-in with participants. Intervals will be based on the date of enrolment. Calls will be permitted to occur within 3 days of the interval date for weeks 1, 2, 3, & 4 and within 7 days for weeks 8 and 12.

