3.4. Interventions

The interventions for this study will consist of dietary supplements for participants in the treatment arm and a placebo for those in the control arm. Three vitamins and one mineral will be included in the intervention for those in the treatment arm – vitamin D3, vitamin C, vitamin K2, and zinc. Upon enrolment and randomization, participants will be provided either dietary supplements or placebo by the study staff. Study interventions are to be started as soon as possible after enrolment and randomization and will continue for 21 days. Participants will be responsible for taking their doses and will be required to return all unused study product to the CHI or their local pharmacy to be properly destroyed. Phone calls will be made to participants at weeks 1, 2, 3, and 4 post-enrolment to check in and inquire about compliance and potential side effects.

All pill bottles will bear labels that comply with Health Canada Regulations. These labels will be in both official languages and contain the expiry date, storage conditions, lot number and the name and address of the manufacturer. An additional statement will be added to each label indicating that it is an investigational product to be used only by a qualified investigator, the trial's sponsor name and address, and protocol code. All study products will be packaged in sealed bottles. Participants will be instructed to store all products as indicated on the product label in a location that is out of reach of children and not to use if the seal is broken. Product accountability records will be maintained to track dispensation, returns and destruction of the study product, and will be maintained by the study staff at the Centre for Health Innovation (CHI). Product inventory will be stored as indicated on the label with daily temperature monitoring.

Information regarding all investigational products, including dosing, timing, absolute contraindications and rationale for use, is summarized below and in section 3.5.

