6.2.1.2. Symptom Severity & Duration

Symptom severity will be conducted using an area under the curve approach comparing the difference in total symptom scores over the 21-day intervention period between both arms. This gives a score range of 0-882 for each participant (i.e., 0-42 each day for 21 days). As a secondary analysis, we will compare the severity of each symptom individually using the same area under the curve approach. Scores for each symptom will range from 0-63 (i.e., 0-3 each day for 21 days). The incidence of severe symptoms (i.e., reporting a “3” for any symptom) will also be compared between arms throughout the intervention period.

The symptom duration analysis will compare the median time to symptom resolution from the start of the intervention period (or the first onset of symptoms if no symptoms were present at the start of the intervention period) up to the end of the intervention period (day 21) between both arms. Symptom resolution will be defined as a zero in all categories with no relapses.

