7.2. Collection and Reporting

AEs will be collected for each participant using the Common Terminology Criteria for Adverse Events (CTCAE) version 5.0. AE collection will begin following the start of the study intervention and will cease 1 week after the intervention is stopped. The exception will be AEs subject to expedited reporting to Health Canada or local REBs (defined below), in which case the AE(s) in question will be followed until completion.

Participants in both arms will be asked about adverse events each week while they are on study (day 7, 14, 21, and 28).

Adverse events will be reported to local REBs according to local requirements. Normally this would include timely reporting for events that are deemed to be unexpected, serious, and related to the study intervention. All other adverse events will be reported to the REB only in the annual renewal report. The frequency and nature of serious adverse events will be documented and reported to the DSMB.

All serious adverse drug reactions will be reported to the TPD and NNHPD. These adverse events are subject to expedited reporting. The sponsor will notify both directorates as soon as possible but no later than 7 calendar days after the sponsor becomes aware of the event for fatal or life-threatening events, and no later than 15 days after becoming aware of non-fatal/non-life threatening events. Within 8 days after having informed the NNHPD and TPD of a serious unexpected adverse drug reaction, the sponsor must submit a report as complete as possible that includes an assessment of the importance and implication of any findings. The final report should include relevant previous experience with the same or similar health products.

Medical and scientific judgment should be exercised in deciding whether expedited reporting is appropriate in other situations, such as important medical events that may not be immediately life-threatening or result in death or hospitalization but may jeopardize the participant or may require intervention to prevent one of the other outcomes listed in the definition above. These should also usually be considered serious. Examples of such events are intensive treatment in an emergency room or at home that does not require inpatient hospitalization or other severe adverse events that do not meet the criteria for being serious.

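### Calls run from enrolment but the AE window and diaries run from the start of treatment, with no common Day 1, so the week-4 AE enquiry can come before the AE window closes

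*Combined protocol and SAP*

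**What the plan says.** **Enrolment clock.** Section 3.7.1 says of the follow-up calls: "Intervals will be based on the date of enrolment". Section 3.4 agrees: "Phone calls will be made to participants at weeks 1, 2, 3, and 4 post-enrolment". The tolerance is also in 3.7.1: "Calls will be permitted to occur within 3 days of the interval date for weeks 1, 2, 3, & 4".

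**Treatment clock.** Under Section 3.7 the EQ-VAS and symptom diaries are completed on each of the 21 treatment days. The duration analysis in Section 6.2.1.2 will "compare the median time to symptom resolution from the start of the intervention period", with symptom onset as the origin for anyone symptom-free at that point. Section 7.2 states: "AE collection will begin following the start of the study intervention and will cease 1 week after the intervention is stopped".

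**Link between the clocks.** Section 3.4: "Study interventions are to be started as soon as possible after enrolment and randomization and will continue for 21 days". Section 4.5 repeats the aim of an early start. Neither sets a maximum delay. Section 3.1 describes the 21 days as following enrolment and randomization, which could be read as a single clock.

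**Table 1.** Dosing, diaries, EQ-5D-5L and calls share the Day 7, 14 and 21 columns, after a baseline column that precedes the intervention and holds randomization. Adverse events are an item of every call, including weeks 8 and 12. Section 7.2 lists AE enquiries only on days 7, 14, 21 and 28, and gives no anchor for those days.

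**Delayed return to usual health.** Section 3.7 says this is "Measured through follow-up calls with participants after the treatment period has ended", at weeks 4, 8 and 12.

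**The concern.** Screening and consent take place by phone and electronic signature, and product is taken at home, so first dose need not fall on the enrolment date. Once the dates differ, a call labelled day 21 or week 4 no longer falls on that day of treatment, although Table 1 presents the two as the same.

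Three things are exposed:

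- completeness of AE collection in the last days of its window;
- how long after treatment the week-4 call for delayed recovery is made;
- if EQ-5D-5L follows the calls, the number of treatment days behind each of its time points. Section 6.2.2 compares these between arms with unadjusted t-tests, so variable timing adds noise.

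**Working it through.** **Inputs.** 21 treatment days (Section 3.4), assumed uninterrupted; AE window to 7 days after stopping (7.2); week-4 call due on enrolment day 28, within 3 days, so day 25 to day 31 (3.7.1). The delay g, in days from enrolment to first dose, is not in the documents. I assume 1 to 5 and also show 0. Enrolment is day 0.

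**The plan's own figure.** With first dose as day 1, the AE window closes on day 21 + 7 = 28, which matches the last AE enquiry in 7.2. In days since enrolment this match holds only at g=1.

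**Formulas, in enrolment days.**

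- Last dose: g + 20.
- AE window closes: g + 20 + 7 = g + 27.
- Days unasked after an on-time call: (g + 27) - 28 = g - 1.
- After the earliest permitted call: (g + 27) - 25 = g + 2.
- After the latest permitted call: (g + 27) - 31 = g - 4.
- Negative values count as 0.

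| g | Last dose | AE window closes | Unasked: earliest call (day 25) | Unasked: on-time call (day 28) | Unasked: latest call (day 31) |
|---|---|---|---|---|---|
| 0 | 20 | 27 | 2 | 0 | 0 |
| 1 | 21 | 28 | 3 | 0 | 0 |
| 2 | 22 | 29 | 4 | 1 | 0 |
| 3 | 23 | 30 | 5 | 2 | 0 |
| 4 | 24 | 31 | 6 | 3 | 0 |
| 5 | 25 | 32 | 7 | 4 | 1 |

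If enrolment is counted as day 1 instead, the window closes one day later and the on-time shortfall is g rather than g-1. The late call then absorbs delays up to 3 days rather than 4.

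**Week-4 call against dosing.** An on-time call falls on or before the last dose only if g + 20 ≥ 28, that is g ≥ 8, outside the assumed range. The earliest permitted call does so if g + 20 ≥ 25, that is g ≥ 5, and at g=5 only on the last dosing day.

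**EQ-5D-5L, only if it follows the calls.** Enrolment day k is treatment day k - g + 1. The on-time week-1 assessment (k=7) is treatment day 7 at g=1 and day 3 at g=5. At g=5 the earliest permitted one (k=4) precedes first dose on day 5. The on-time day-21 assessment falls g-1 days before the last dose.

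**Later calls as a backstop.** Under Table 1 the next AE enquiry is the week-8 call, on enrolment day 56 if on time. That is 56 - 28 = 28 days after the window closes at g=1, and 56 - 32 = 24 days at g=5.

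**The case against.** The strongest reply is that this is mainly a labelling gap. Anchoring follow-up to enrolment is a legitimate choice under intention to treat, because first dose comes after randomization and some participants may never start. The 3-day tolerance absorbs delays of up to 4 days if the call is made late. Events near the end of the window could still be reported at weeks 8 and 12 under Table 1, and hospitalizations are tracked separately through the electronic record (Section 3.6.1).

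Much of this stands. A reader might infer that any start delay makes the contacts too early. The arithmetic does not support that: at g=1 an on-time call loses nothing. Nor does an on-time week-4 call fall during treatment at any delay in the assumed range. A reader might also take it that the day-21 EQ-5D-5L is completed before dosing ends. The enrolment rule in 3.7.1 is written for calls, Table 1's footnote names EQ-5D-5L completion separately, and its anchor is never stated, so that consequence is conditional.

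What does not stand is that the plan already handles the problem. No rule tells staff to call late when dosing began late. Section 7.2 ends both AE enquiry and AE collection before weeks 8 and 12, so Table 1's backstop conflicts with it and would rely on recall after about four weeks. The single-clock reading of Section 3.1 would leave a late starter with fewer than 21 treatment days, against 3.4, so those passages must be reconciled in any case.

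**Conclusion.** The point holds for AE completeness and consistent timing of secondary assessments. For assumed delays of 1 to 5 days, the week-4 call leaves 0 to 4 days of the AE window unasked if on time, 3 to 7 if made as early as permitted, and 0 or 1 if made as late as permitted. The two-sided tolerance is a fault even with a same-day start: a day-25 call comes 2 days before the window closes. The actual size depends on a delay the documents do not give, and on 21 uninterrupted treatment days.

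A reader might infer a threat to the primary result. The documents do not support one: the EQ-VAS and symptom areas under the curve and time to resolution come from daily diaries, which call timing does not shift. In a randomized, double-blind trial nothing suggests that the delay differs by arm, so the expected cost is noise and incomplete AE capture rather than bias. The change is worth making because it is nearly free.

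**What to change.** - Define Day 1 once: the date of first dose or, for anyone who never starts, the day after randomization.
- Count calls, EQ-5D-5L, diaries and AE enquiries from Day 1, and say so in Sections 3.4, 3.7.1 and 7.2 and in the Table 1 column labels. Changing 3.7.1 alone would leave it in conflict with 3.4.
- Make the week-4 call window one-sided, on or after day 28.
- Reconcile Section 3.1 with 3.4 on what the 21 days are counted from, and Table 1 with 7.2 on whether AEs are asked about at weeks 8 and 12.
- Record both enrolment and first-dose dates. Section 4.5 already monitors days from symptom onset to starting product, so the first-dose date is needed anyway.

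The on-time week-4 call then coincides with the close of the AE window whatever the delay, for anyone completing 21 uninterrupted days. The earlier contacts keep their 3-day tolerance, so a day-21 EQ-5D-5L could still be completed on day 18, but that spread would no longer grow with the delay.

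The cost is a few sentences and table labels. Call reminders can be set only after first dose is confirmed, and a rule for non-starters is needed. No visits are added and no dosing changes.
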